7.2.10 Daily Cigarette Diary and Daily E-cig Diary

During the entire study period (not including the follow-up phase), participants will be required to record the number of cigarettes smoked per day and study product use (after randomization) on provided paper-based diaries. Participants will be given an E-cigarette Daily Diary that also includes a space to record any cigarettes smoked. Researchers will enter daily diary totals in REDCap at each study contact for all days in the study. Daily diaries will stop after Visit 3 and participants will only be asked about past 7 day use at subsequent visits.

7.2.11 Unscheduled Visits

If a participant requires additional study product (e.g., e-cig pods), or if the SREC product fails, they may call the research center to schedule a time to obtain additional products (in-person). Product may also be shipped to the participant's home if they are not able to come to the study center in a timely manner.

7.2.12 Appointment Reminders

Phone call and/or text message reminders will be used throughout the study to remind participants of their next visits (approximately 1-2 days prior). In addition, when COVID protocols apply, participants will be sent a link to their phone or email to complete COVID symptom screener 24 hours before the visit. Also, visit time/date confirmation and study center directions will be emailed to the participant prior to Visit 1. (SEE APPOINTMENT REMINDER LETTER ATTACHMENT). For those without email, the first visit instructions will be explained to the participants who allow us to contact them through phone and text messaging, the study team will be using Google Voice to call or text participant reminders of the study visit and reminders to complete the study surveys with the REDCap survey link. Google Voice is phone service that allows researchers to communicate with participants without revealing their personal phone numbers. The study team will save participants phone number with their study ID. Participants will be told not to share PHI through this phone number.

7.2.13 Biospecimen Processing

All urine samples collected will be analyzed in the research lab. These samples will be analyzed for NNAL, CYMA, MHBMA3, 3HPMA, creatinine, 8-isoprostanes, and cotinine.

7.2.14 Data Collection via Phone

If participants are unable to attend an in-person study visit, the researcher will attempt to collect data over the phone. Participants will not be compensated for data provided through this method.

7.2.15 Missed Visit Procedures

Participants will be called at least once to reschedule a missed Visit 1. For participants who do not show up for in-person Visits 2-3, up to 3 phone/text/email attempts will be made to contact them to reschedule their appointment. After the 3rd attempt, a letter will be emailed to the address on file informing them that the study team has been trying to reach them and asking them to contact the study center to reschedule. No further attempts to contact the participant will be made after the letter is sent (see study documents for letter).

7.3 Duration of Participation

Participants who complete all phases of the study will participate in the study for a total of 10 weeks.

7.4 Test Article(s) (Study Drug(s) and/or Study Device(s))

7.4.1 Description

The e-cig used will be a Standardized Research E-Cig (SREC). The SREC product is a pod-based device and comprises a replaceable pre-filled liquid reservoir ("pod") and a rechargeable power supply unit. The SREC was designed for reliability and user convenience. Important features include: breath actuation, a tank and battery of sufficient capacity to satisfy smokers for >1 day on a single unit, primary packaging of the tank with excellent oxygen and water vapor barrier properties to ensure a long shelf life, and power control to maintain a constant aerosol output over the lifetime of the tank and battery charge. Preliminary pharmacokinetic data on the SREC with 58 mg/ml nicotine liquid suggests that 5 minutes of puffing (10 puffs) produces a C_{max} of just over 21 ng/ml at around 5 minutes, and preliminary studies of subsequent ad-lib use suggest blood nicotine levels around 15 ng/ml. Both the 58 mg/ml (5%) and 0 mg/ml (0%) nicotine pods contain 1.9 ml of liquid, 50:50 propylene glycol: glycerin based with a tobacco flavor.

7.4.2 Treatment Regimen

Participants will be randomized to receive either a 0 mg/ml or 58 mg/ml nicotine liquid to be used with the SREC device. They will be told to use the SREC ad libitum as a replacement for conventional cigarette use.

7.4.3 Method for Assigning Subject to Treatment Groups

Participants will be randomized to one of two conditions: a SREC with pods containing 0 mg/ml nicotine content (placebo) or a SREC with pods containing 58 mg/ml nicotine content (nicotine). Using a 1:1 allocation ratio, the randomization template was created by the study's unblinded statistician via blocked randomization. The Randomization Module in REDCap will assign each participant to a 6-digit alpha-numeric code upon randomization at Visit 1. This code is unique to each randomized participant and is accessible to all study personnel. This code provides a blinded reference which identifies the SREC-device kit to be assigned and associated with the pharmacy device distribution. The utilization of this alpha-numeric code allows study personnel to be blinded from the nicotine dose while simultaneously distributing the devices to the

participants. The master blinded randomization file links each alpha-numeric code to a randomized nicotine dose. This file does not exist in REDCap, is not stored on any shared accessible network drives, and is not accessible to any blinded study personnel (except in the event of an emergency situation that requires the breaking of the blind).

In the event that REDCap is down during a Visit 1 and a participant is ready to be randomized, the REDCap Randomization downtime procedure should be followed and implemented. This means that pharmacy will continue their list and no data will be entered into REDCap until participant can be randomized in the system.

7.4.4 Subject Compliance Monitoring

Participants will be given daily diaries to complete on which they will record the number of cigarettes smoked and number of e-cig puffs each day. Participants will be given detailed instructions on how to complete the logs. Questions will be asked at each contact to review participants' logs and to verify their daily conventional cigarette and e-cig use. Participants will also be asked to self-report their other tobacco use including products such as cigars, pipes, chew, snus, dip, hookah, and dissolvable tobacco. Exhaled carbon monoxide measurements and urine samples will be collected throughout the study to verify smoking intensity, nicotine, and cotinine levels.

Participants will be asked to return all of their used and unused study products and to bring their e-cigs to the study visits following randomization. At each of these visits, study staff will review the used pods to get an estimate of how much e-cig liquid was used by the participant.

7.4.5 Blinding of the Test Article

The SREC products will be received by unblinded staff. The pods will contain a barcode, which will be scanned by the unblinded staff to determine the numeric code. The unblinded staff will match the numeric code on the pod to a list linking the numeric code with the allocation, active (58 mg/ml) or placebo (0 mg/ml).

Unblinded staff will appropriately package the pods and SREC parts into packs/kits for the participants. The kits will have assigned numbers, and the participants will be randomly assigned to a kit number at the randomization visit (Visit 2). The blinded researcher will not be involved in the packing and labelling of the kits and will only have access/knowledge of the alpha-numeric kit code assigned – but will remain blinded to the dose that each kit corresponds to. Only the study statisticians and packing/labeling personnel will be unblinded to the dose that each kit is linked to via randomization. All other study personnel, including lab staff, will remain blinded until the last randomized participant completes Phone Call #5 in the study follow-up phase at Week 10.

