7.2.7 Follow-Up Phase – Phone Contact #5 (Day 70 ± 7 days)

During this follow-up phone contact, past 7 day study product and cigarette use will be collected via a 7 day timeline follow-back (TLFB) procedure (meaning that participants will be asked to recall their use from memory for the past 7 days), adverse events or changes to concomitant

medications will be documented, and participants will be asked to answer the measures indicated in the Time and Events Table.

7.2.8 Follow-up Phase – Interview Visit 4 (Day 70 + 60 days) (Optional study visit)

At consent, participants will be given the option to be considered to participate in an additional study procedure, a structured interview about their experiences using the e-cig device to stop smoking.

Participants who consent to the optional part of the study will be contacted by the researchers after completion of the study (after Visit Ph #5) to schedule an additional study visit to complete the interview. Only participants who complete the study (ie. Complete Ph #5) will be contacted.

Participants who are contacted and who agree to participate in the interview will be contacted to schedule an in-person visit at the study center. The interview will take place via ZOOM and will last approximately 30-60 minutes. Interview questions will be related to the participant's experience using the e-cig and attempting to switch completely from cigarettes. All interviews will be recorded and transcribed. In addition, participants will be asked to provide their past 7 day cigarette (via 7 day TLFB) and e-cigarette use.

- We plan to recruit 40 participants to complete the interview part of the study. We plan to recruit participants who met the following criteria:
- 8 participants who successfully switched and were randomized to the Omg/ml group
- 12 participants who successfully switched and were randomized to the 58mg/ml group
- 8 participants who did not successfully switch and were randomized to the Omg/ml group
- 12 participants who did not successfully switch and were randomized to the 58mg/ml group

Successfully switching for the interview part of the study will be defined by no cigarette use reported in the past 7 days reported at Visit 3 and Visit Ph #5 and a CO < 6ppm at Visit 3.

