The first participants who meet the outlined criteria will be contacted by the researchers. We will continue to recruit participants for each category until all interviews for that category is completed. The interviews will be completed by blinded researchers but the management of the recruitment of participants for the interview will be managed by an unblinded study team member. This will ensure that recruitment for each category is correctly executed.

7.2.9 Follow-up Phase – Product Use Visit (Day 70 + 60 days) (Optional study visit)

At consent, participants will be given the option to be considered to participate in an additional study procedure. Participants who consent to the optional part of the study will be contacted by the researchers after completion of the study (after Visit Ph #5) to schedule the additional visit.

Participants who meet the following criteria will be contacted:

- Complete the study (ie. Complete Ph #5)
- Still using a nicotine containing product at Ph #5

The first participants who meet the outlined criteria will be contacted by the researchers. We will continue to recruit participants this optional visit until 10 participants have completed.

For the procedure, participants will be asked to use the SREC product in the lab while blood is collected. First, participants will be asked to abstain from any nicotine containing products for at least 14 hours before attending the visit. Once they arrive at the study center, a CO will be collected to verify abstinence (CO < 15 ppm to be eligible). Then, participants will complete

baseline questionnaires about withdrawal and craving. Then, participants will be given the SREC device with a 5% pod to use in the lab in a standard manner of 1 puff every 20 seconds for 14 puffs total (4 minutes, 20 seconds). Blood will be collected via an intravenous line at baseline and then 1, 2, 4, 6, 8, 10, 12 and 15 minutes after the first puff on the device. After the last sample is collected, the IV will be removed and participants will be asked to complete another CO measurement and to complete questionnaires about withdrawal and craving as well as questionnaires about their experience with the product.

	Time and Events Table									
	Baseline Phase	Switching Phase Follow-up Phase								
Study Week Number	0	1	2	3	4	5	6	10	10	10
Study Day	0	7	14	21	28	35	42	70	70	70
Study Visit Number	1	Ph #1	Ph #2	2	Ph #3	Ph #4	3	Ph #5	4 (ZOOM)	6
Measures/Questionnaires										

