We will strive to minimize the number of missing values by rigorous follow-up with the study subjects. In spite of this, we still anticipate some missing values in the final datasets. Our basic tool to address this problem is multiple imputations. More specifically, if a variable is missing at V1, it will be imputed from the distribution of that variable of non-missing subjects. Due to the randomization at V1, non-missing subjects from both arms will be used for the distribution. For values missing at V3 (6 weeks after randomization), but non-missing at V2, the value collected at V2 will be carried forward in time via the LOCF (Last Observation Carried Forward) approach. For any instance where the participant remained in the trial, but did not provide data values at either post-randomization visit (V2 or V3), that case will be excluded from the analysis (modified ITT).

For some scenario, the missing values can be imputed by some reasonable assumptions. If a participant dropped out of the study prior to Visit 3 without providing Visit 2 data for the outcome, a 'worst-case-scenario' assumption will be made – assuming that the participant reverted back to exclusive smoking of cigarettes upon dropping out of the trial. Under this assumption, their Visit 2 baseline value will be carried forward to Visit 3. See the table below for a detailed outline of these methods:

V1	V2	V3	V` Baseline Result	V3 Endpoint Result	Mechanism of Missing		
+	+	+	Use directly Use directly		N/A		
+ + -			Lise directly	Impute V3 via LOCE from V2	Dropped out between V2 and V3		
	•	-			Missing V3 due to item non-response		
+	-	+	Use directly	Use directly	N/A		
-	+	+	Impute the V2 value from the overall sample distribution	Use directly	N/A		
			Use directly	Impute V3 via LOCF from V1	Dropped out between V1 and V2 Assume 'Worst-Case- Scenario'		
+	-	-	Excluded from Analysis (N	Dropped out between V2 and V3 Item Non-Response at V2			
			Excluded from Analysis (N	Completed the Switching Phase Missing V2 and V3 due to item non-response			
	Impute the V1 value		Impute the V1 value	Impute V2 via LOCE from V2	Dropped out between V2 and V3		
-	T	-	distribution		Missing V3 due to item non-response		
-	-	+	Impute the V1 value from the overall sample distribution	Use directly	N/A		
-	-	-	Excluded from Analysis (Modified ITT)				

Stratified Imputation Approach:

(+) = non-missing data(-) = missing data

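### Section 7.4.5 lets the blind for lab and study staff end at the last randomized participant's week-10 call, although blinded interviews follow that call and nothing requires NNAL assays or data cleaning to be finished first

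*Combined protocol and SAP*

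**What the plan says.** Section 7.4.5 names the statisticians and the packing and labeling personnel as unblinded. For everyone else it sets one end point: "All other study personnel, including lab staff, will remain blinded until the last randomized participant completes Phone Call #5".

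Section 7.2.7 schedules that contact as "Phone Contact #5 (Day 70 ± 7 days"). Section 7.2.8 then adds "Interview Visit 4 (Day 70 + 60 days) (Optional study visit") and restricts who may be approached: "Only participants who complete the study (ie. Complete Ph #5) will be contacted". It also requires that "The interviews will be completed by blinded researchers". Recruitment continues until each of four categories, defined by arm and switching status, is filled (40 interviews in all).

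The primary endpoint (section 1.2) is creatinine-corrected urinary NNAL at week 6. Section 7.2.13 says which analytes will be measured and where, but not when. Section 8.3 makes the handling of missing outcomes depend partly on why they are missing. One class of case is excluded: "For any instance where the participant remained in the trial, but did not provide data values at either post-randomization visit". Some dropouts instead have the baseline value carried forward. No section mentions a database lock.

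**The concern.** A blind normally ends when no remaining step can be influenced by knowing the arm. Here it is tied to one participant's phone call. Three kinds of work can still be open at that moment: the interviews, other participants' week-10 calls, and the laboratory and data-cleaning decisions behind the week-6 results.

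The interviews raise a consistency problem. For the last enrollee, section 7.2.8 asks for a blinded interviewer at a time when section 7.4.5 no longer promises one. The late week-10 calls matter because the Aim 3 outcomes (continued abstinence and e-cig use) are self-reported to study staff. The laboratory and cleaning decisions matter most for the main result. Whether to repeat an assay, drop a sample, or record a missing value as dropout or as item non-response can change who is analyzed and with what value.

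**Working it through.** The plan gives no figure to reproduce on this point, so the check compares its own time windows. Days are counted from each participant's randomization at Visit 1.

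**Inputs**
- Visit 3, with the week-6 urine sample: Day 42 −7/+14 (section 7.2.6), so Day 35 to 56.
- Phone Contact #5: Day 70 ± 7 (section 7.2.7), so Day 63 to 77.
- Interview: Day 70 + 60 (section 7.2.8), read as open until Day 130, and only after that participant's Phone Contact #5.

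**Interviews against the end of the blind**
- Last enrollee, call on Day 77: 130 − 77 = 53 days of interview window remain.
- Last enrollee, call on Day 63: 130 − 63 = 67 days remain.
- Any interview with the last enrollee must follow the stated end of the blind.
- Someone randomized d days earlier still has open window after the last enrollee's call if 130 − d exceeds the call day. That means d up to 52 (call on Day 77) or up to 66 (call on Day 63).

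**Week-10 calls against the end of the blind**
- On the last enrollee's clock, a participant randomized d days earlier can be called as late as Day 77 − d, while the last enrollee can be called as early as Day 63.
- 77 − d > 63 requires d < 14, so d can be up to 13 days.
- Section 8.2 allows for as much as 30% dropout. If the last randomized participant never completes the call, section 7.4.5 defines no end to the blind at all.

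**Assays against the end of the blind**
- Last enrollee with urine on Day 56: 63 − 56 = 7 to 77 − 56 = 21 days until the call. On nominal days, 70 − 42 = 28.
- For someone randomized d days earlier, add d. The short interval therefore applies only to the final enrollees.
- The number of samples exposed depends on an assay schedule that the plan does not give. If assays run continuously, it is the last few samples. If they are batched after follow-up (an assumption), it could be all of them.

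**What one coding decision can move**

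This is an illustration, not an estimate. Take section 8.2's post-treatment mean of 80 and baseline mean of 225 with n = 84, and suppose k people are coded so that baseline is carried forward rather than being excluded. The unadjusted arm mean becomes (84 × 80 + k × 225) / (84 + k).
- k = 1: 6,945 / 85 = 81.7, a shift of 1.7, or about 5% of the design difference of 35.
- k = 3: 7,395 / 87 = 85.0, a shift of 5.0, or about 14%.
- k = 5: 7,845 / 89 = 88.1, a shift of 8.1, or about 23%.

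The values of k are assumed. The planned model adjusts for baseline, which would change these shifts.

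**The case against.** The case on the other side is substantial.

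- **The date is a minimum.** Section 7.4.5 says how long staff stay blinded at least; it does not order the codes released that day. Section 7.4.3 keeps the master file out of REDCap and away from blinded staff, and section 21.4 limits access by role. This stands: a reader might infer a planned release on the day of the call, but the text does not say so.
- **The interview rules can both be met** if interviewers are simply not told. The interviews are optional and feed no listed endpoint. The quotas of 12 and 8 switchers may also fill early: section 8.3 expects roughly 33 and 16 abstainers, under a somewhat different definition. This stands as to likelihood, but nothing ensures it, and the two sections still need to be reconciled.
- **Most outcome data are fixed early.** Contact data and diaries are entered at each contact (sections 7.2.10 and 10.3), abstainer status follows a set rule, and missing data follow a table (section 8.3). This largely stands. The missingness rule is not fully mechanical, however. The text carries baseline forward for anyone who leaves before Visit 3 without Visit 2 data, while the table excludes those who leave between Visits 2 and 3 with item non-response at Visit 2. Someone has to settle such cases.
- **NNAL is a quantitative assay**, and no section describes discretionary re-runs. This limits the likely bias.
- **The statisticians are already unblinded.** If they derive abstainer and missingness status, a later date for other staff protects less. This stands, and limits what the change can achieve.

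Two further inferences are tempting but not supported. The unblinded person who manages interview recruitment need not be an extra role, since that person may be one of those listed in section 7.4.5. Nor are premature allocation letters shown: section 13.0 sends them only once the trial has completed.

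**Conclusion.** The point holds as a weakness in how the end of the blind is defined. By the plan's own windows, the stated end can precede required blinded interviews by up to 53 to 67 days for the last enrollee, and can precede the week-10 calls of people randomized up to 13 days earlier. Nothing requires the primary assays or data cleaning to be complete by then.

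The likely effect on NNAL is small. The exposure lies in re-run, exclusion and missingness-reason decisions, and its extent depends on an assay and cleaning schedule that the plan does not state. A reader might conclude that the NNAL samples will be assayed unblinded. The documents do not support that: they are silent on timing, and the claim that no sample is protected would need an assumed end-of-study batch. The interview conflict is the firmest part textually, but it does not reach the primary result.

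**What to change.** Replace the end point in section 7.4.5. Lab and other study staff should remain blinded until all of the following are done:
- every participant's Phone Contact #5 is complete or formally closed out;
- all urine assays are final, including any repeats;
- abstainer status and the reason for each missing outcome are recorded;
- the database is locked.

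Add that interviewers stay blinded until the last interview is done. Keeping this as a separate condition means that an optional interview series does not delay unblinding of everyone else.

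The cost is a short protocol edit and a later date at which staff learn the allocation, by some weeks. Sample size, visits and analysis models do not change.
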